at 2.1 hours and for the metabolite—norketamine at 1.2 hours—this from a ketamine study in children indicating the safety of this medicine (Herd et al 2002). Samples will be collected prior to injection for baseline measurement, and timed at 3, 6, and 9 hour intervals--choosing the maximum half-life duration. Two dosages will be administered: 0.5ml/kg and 1.0ml/kg. administered Intramuscularly (IM). Each administration will be separated by a minimum of 3 days and preferably one week.

The study subjects participants to greater than minimal risk because the protocol design calls for administration of IM ketamine. While the safety of IM ketamine administration is well established over decades of use, participants will be provided with full information on risks.

SEE PACKAGE INSERT FOR THIS MANUFACTURER—ATTACHED.

The IM route confers rapid onset—2-5 minutes for effect and a reliable approximate 95% absorption of ketamine. The dosage range for a 50 kg woman amounts to 25-50mg and for a 70kg woman 35mg-70mg, both quantities well within commonly used therapeutic administration of IM ketamine for depression and other psychiatric diagnoses (Dore et al, 2019).

While psychiatric use of ketamine may well exceed 1.0 mg/kg, blood concentrations of ketamine for anesthetic use have tended to follow a linear pattern of concentration, enabling estimates of concentration in breast milk, should there be a decision to exceed 1.0mg /kg IM in clinical practice.

Inclusion Criteria

Obtained by Interview/Self-Report

- • Age 21-45
- • Postpartum with established lactation for a minimum of 3 months.
- • Ability to pump breast milk and to provide a reservoir for infant feeding prior to the study; or acceptance of bottle feeding by the infant.
- • In good health—normal BP/P; afebrile-temp ascertained; review of systems by MD; absence of diagnosed illnesses.
- • Not pregnant--Pregnancy tested for before each administration by urine assay.

Exclusion Criteria:

- • Hypertension with a BP greater than 145/90
- • Subjects must be offAbsence of all psychiatric medications specifically; medications and supplements, or evaluated by the PI for non-interference
- • No alcohol or other substances such as marijuana for 72 hours or more.
- • Weight <50kg or > 90kg.
- • Pregnancy

Method of Subject Identification and Recruitment

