This study will assess if the rapid elimination of ketamine facilitates a short and tolerable suspension of breastfeeding. If the study determines that significant amounts of ketamine remain in breast milk after 9 hours and 3 intervals, a decision will be made to add further intervals for assessment. The collection at 3 hour intervals will continue until ketamine levels are undetectable.

No hazardous substances or procedures are involved

Pumping of breast milk will be performed by the subjects, collected, and preserved as per the lab's criteria. Every attempt will be made to collect milk in volume. The study will provide a pump for collection to each participant

Subjects may stay at the clinic for the duration of the collection , or may be provided with instructions and collection materials for at home pumping if the duration is prolonged beyond 9 hours. As much as possible, tThe samples will be collected by the next day.

Subjects will refrain from eating and drinking 3-4 hours before receiving ketamine, this to prevent stomach contents that may contribute to nausea, and reduce any risk of aspiration. Subjects are permitted one cup of coffee if they are caffeine dependent, or juice or water at 3-4 hours prior. Subjects will provide consent for fasting prior to its initiation verbally and later fully in person at the clinic.

A urine pregnancy test will be conducted prior to each administration of ketamine.

A first subject in the study will have milk collected at 0, 3, 6, 9, 12 and 15 hours to determine if these intervals are sufficient to characterize a basic pharmacodynamic profile. If there is a negligible quantity in the samples as the time frame proceeds, the lab will not analyze subsequent samples. Once determined, the study will proceed with the remaining 3 subjects at the intervals projected from the first subject

Two dosages will be administered: 0.5ml/kg and 1.0ml/kg. Intramuscularly (IM). Each administration will be separated by a minimum of 3 days and preferably one week. Each session will follow the same process and procedure as described herein and occur at the study site.

PROCEDURE TIMING CHART

HOUR	PROCEDURE
-30 minutes	Arrives at Study Site Pregnancy Test Review of IC and Fasting with Consent
-!5	BP, HR, Review of Systems
0 Hour	Zero Time Pump
15	IM 0.5mg/kg; or Second Session 1.0mg/kg
15-60	Support for Subject who is reclining on sofa with eyeshades and ambient music

1 hour	BP, HR

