1-3 hours	Support for subject and integration of experience
3 hours	BP, HR, Second Pump
3-6 hours	Subject relaxing at Study Site
6 hours	Third Pump
9 hours	Fourth Pump
12 hours	Fifth Pump if necessary (as per procedure)
Home	Milk has been quantified for volume at each pump and an aliquot labelled, saved and refrigerated. If subject has gone home earlier—at 6 hours or later, subject will be contacted to pump at the assigned intervals and an aliquot refrigerated for pickup and delivery to the clinical lab for analysis.

Safety: Administration of ketamine will occur in office premises and with standard of care safety equipment available. This includes CPR trained personnel, ambu bag, defibrillator and a suction device. MDs will be present on site throughout and will administer the injections.

Injections are provided with a 25 gauge, 1 inch needle using ketamine in a sterile 100mg/ml concentration. Total volume of ketamine fluid will be less than 1 cc. Occasionally, there may be a slight bleed from the injection site. There may be mild ache at the injection site for up to a few hours. Injections are intra-muscular and into the deltoid or buttocks regions.

Subjects will be provided in advance for preliminary screening with our standard intake form to assess current and previous illnesses, psychiatric conditions, and emergency contacts, etc. This will enable Investigators to screen potential subjects prior to enrollment—as is our general practice. The Informed Consent will be provided along with the Intake Form for review by the subjects prior to making a decision to proceed with the study intake process.

At Intake, subjects will discuss, and make a decision to sign, or , the Informed Consent.

HIPAA confidentiality will be maintained throughout. Subjects will be given a numerical designation for all materials, other than the written forms discussed herein. All written and confidential materials will be stored in a locked file on premises available only to the Investigators.

No hazardous substances or procedures are involved

Methods

Quantitative analysis of ketamine will be performed by [name] PhD, Professor of Laboratory Medicine at UCSF School of Medicine and [name] at UCSF.

- 1) Lab will prepare a standard for analysis of ketamine and its principle metabolite norketamine in breast milk. The half-life of ketamine is 2.1 hours, and that of norketamine 1.2 hours (Herd et al 2007). The study will view the half-life as being a conservative 3 hours.

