1. 5) Each aliquot will be labelled with coded subject designation, concentration of ketamine administered, date, and interval. The lab will be provided with the actual quantity of ketamine administered to each subject at the 0.5 and 1.0mg/kg levels and the weight of each patient in kgs.
 - 1)
1. 6) The Lab will provide the data to KRF in formats suitable for journal publication.

INTAKE FORM ATTACHED

AS PREVIOUSLY INDICATED THERE ARE NO QUESTIONNAIRES BEING ADMINISTERED— THIS WAS DELETED FROM THE PRIOR REVISION

Inclusion Criteria

- Age 21-45
- Postpartum with established lactation for a minimum of 3 months.
- Ability to pump breast milk and to provide a reservoir for infant feeding prior to the study; or acceptance of bottle feeding by the infant.
- In good health—normal BP/P; afebrile-temp ascertained; review of systems by MD; absence of diagnosed illnesses.
- Not pregnant--Pregnancy tested for before each administration by urine assay.

Exclusion Criteria:

- Hypertension with a BP greater than 145/90
- Absence of all psychiatric medications specifically; medications and supplements, or evaluated by the PI for non-interference
- No alcohol or other substances such as marijuana for 72 hours or more.
- Weight <50kg or > 90kg.
- Pregnancy

Potential Adverse Effects

- • Nausea and vomiting—a less than 5% incidence of intolerability to ketamine.
- • Transient hypertension—BP will be monitored. In clinical practice, and in this age group, this has not occurred with any frequency.
- • Ketamine is a dissociative anesthetic and subjects have a high likelihood of experiencing dissociative effects during the first two hours following ketamine's administration. Generally, the major impact occurs in the first hour, with full recovery to baseline by 3 hours. The Investigators have conducted thousands of sessions in which dissociative effects are part of the ketamine assisted

psychotherapy (KAP) approach, including at much higher doses than those being administered in this study. Subjects may experience, an altered mental state in which there is an imaginative stream of associations, sensations and imagery. There can be anxiety accompanying a shift from ordinary reality. The Investigators have specialized in developing a transformative psychotherapy with utilization of this state and are fully equipped and experienced in dealing effectively with this state. Subjects will be prepared for the possibility of this

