Screening Script: *The Ketamine Research Foundation is conducting a study of the presence and concentration of ketamine in breast milk following two administrations of ketamine by injection intramuscularly. This study is in preparation for use of ketamine as an assisted psychotherapy for women suffering with postpartum depression. If you agree to participate, ketamine will be*

administered to you on two separate occasions based on your body weight. You would spend at least 10 hours at our comfortable offices in San Anselmo under the supervision of MDs and psychotherapists. You would need to pump breast milk on at least 3- 4 occasions at 3 hour intervals. You will be asked to fast for 3-4 hours prior to administration of ketamine to reduce the possibility of nausea which may occur and does occur in a small percentage of patients who receive ketamine. The effects of ketamine may would last for up to 2 hours, one hour of which can be expected to be a significant altered state and you would be lying down for the experience. Payment for participation includes cost of transportation and an initial stipend on acceptance into the study of \$100, and on completion a second \$100 stipend. Ketamine is known for its safety and positive effects on depression and other emotional difficulties. This is not about psychotherapy, but you will receive full attention for any emotional experiences you may encounter. You will be able to have a person of support present and your child as well. You will not be able to breast feed during the study session. To qualify, you need to be in good health, between the ages of 21 and 45, have been lactating for at least 3 months, not be on medication, and have normal blood pressure.

To be interviewed for the study, please email to [contact].

Thanks for your consideration!

[name] MD—Director

Informed Consent

All study subjects will have full capacity to consent. The Informed Consent will be mailed to subjects for their review prior to enrollment. The IC will be presented to subjects by the staff, reviewed for subjects understanding of the IC and what is involved in the study, for discussion and questions and clarification. Subjects may elect to withdraw from the study prior to receiving the first and second injections—without consequence. The IC is attached.

Study subjects will be fully aware that they will not breast feed infants for the period of the study so as not to expose infants to ketamine in breast milk.

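### The timing chart counts hours from the baseline pump, not from the injection 15 minutes later, and no clock times are required that would let the analysis correct for this

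*Combined protocol and SAP*

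**What the plan says.** All references are to the combined protocol and SAP.

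- **Procedure Timing Chart.** Hour 0 is the "Zero Time Pump". The next row, at 15 with no unit, is "IM 0.5mg/kg; or Second Session 1.0mg/kg". Then come a row for 15-60, the one-hour blood pressure and heart rate check, and the 3-hour row, "BP, HR, Second Pump". Further pumps follow at 6, 9 and, if needed, 12 hours.
- **Summary of Research Design.** "Samples will be collected prior to injection for baseline measurement, and timed at 3, 6, and 9 hour intervals". The spacing is justified by half-life, but the origin of the hours is not stated.
- **Procedures.** The text places a blood pressure and pulse reading one hour after administration.
- **Methods, item 5.** "Each aliquot will be labelled with coded subject designation, concentration of ketamine administered, date, and interval". The laboratory also receives the actual dose and body weight. Times are not mentioned.
- **Data Analysis.** The listed variables are age, weight, dosage, milk volume and months of breastfeeding. Time since injection is not among them.
- **Home pumping.** Procedures provides "for at home pumping if the duration is prolonged beyond 9 hours". The chart's Home row covers a subject who leaves sooner: "If subject has gone home earlier—at 6 hours or later". She is to be contacted when each pump is due.

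**The concern.** The study's product is a milk concentration at a stated time after a dose, and the decline from one time to the next. Both need a defined time zero. Half-life has meaning only from dosing, so a reader will take 3, 6 and 9 hours as hours after the injection. On the chart they are not.

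The planned 15 minutes could be subtracted later if everyone kept to the chart. Departures from the chart could not, because nothing requires the actual times to be written down. There are only four women, and the first woman's profile sets the sampling intervals for the other three, so timing errors have little chance to average out. A time that was never recorded cannot be recovered.

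**Working it through.** **Inputs.** Chart times are 0, 15 and then 3, 6 and 9 hours. Methods gives a ketamine half-life of 2.1 h and a working value of 3 h, and states that each pump is a full expression. The 15 is read as minutes because the next row runs 15-60 and is followed by one hour. That run also shows a single continuous clock from the baseline pump. Counting the later hours from the injection would give exactly 3, 6 and 9 h but would break the run.

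**1. Time after dosing** = chart time − 0.25 h.
- Pumps: 3 − 0.25 = 2.75 h, 6 − 0.25 = 5.75 h, 9 − 0.25 = 8.75 h.
- Blood pressure and heart rate: 1 − 0.25 = 0.75 h, or 45 minutes. The Procedures text says one hour.

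**2. Point levels.** With mono-exponential decline, the level at the actual time relative to the stated time is 2^(0.25/half-life).
- Half-life 2.1 h: 1.086, so 8.6% higher.
- Half-life 3 h: 1.059, so 5.9% higher.

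The factor is the same at every pump, so it cancels from the slope and the half-life is unchanged.

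**3. Pooled levels.** A full expression holds milk made since the previous pump. Assume instant absorption, constant secretion and milk that tracks plasma, and let k = ln 2 / half-life. The first expression contains 15 minutes of pre-dose milk, so its ratio to a true 0-3 h post-dose pool is (1 − e^(−2.75k)) / (1 − e^(−3k)). Later samples carry the factor from step 2.

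| Half-life | First sample | 6 h and 9 h samples |
|---|---|---|
| 2.1 h | 0.949 (5.1% low) | 1.086 (8.6% high) |
| 3 h | 0.941 (5.9% low) | 1.059 (5.9% high) |

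**4. Effect on a fitted half-life under step 3.** A log-linear fit to three equally spaced samples has slope (ln C9 − ln C3)/6. The opposite errors flatten it by ln(1.086/0.949)/6 = 0.0225 per hour. At 2.1 h, k = 0.3301, so the fitted rate is 0.3076 and the fitted half-life is 0.6931/0.3076 = 2.25 h, which is 7.3% too long. The same steps at 3 h give 3.28 h, 9.4% too long.

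**5. An unrecorded home pump at 9 h.** The subject is on site for the 3 h pump and may leave at 6 h or later, so suppose that only the 9 h pump departs from schedule. Treat the samples as point values. In the fit to 3, 6 and 9 h the last point has weight (9 − 6)/18, because the squared deviations from the mean time sum to 9 + 0 + 9 = 18. The relative SD of the elimination rate is 3 × SD/18.
- Timing SD 15 min (assumed): 3 × 0.25/18 = 4.2%.
- Timing SD 30 min (assumed): 3 × 0.5/18 = 8.3%.

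**The case against.** The strongest reply is that the planned offset is small, constant and known. Anyone can subtract it, and with point sampling it leaves the half-life untouched. Milk times are never expressly defined as hours after dosing, the label's interval is not said to be nominal, and staff may keep times elsewhere. Data Analysis plans absolute quantities, graphs and correlations, not a half-life for each woman. Subjects at home are to be contacted when a pump is due.

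Much of this stands, and it limits the point. It does not supply a time origin, remove the conflict over the one-hour check, or create a requirement to record times. A prompt to pump is not a record of when she pumped. Methods also sets out to document the pharmacokinetics fully, so a decline rate is a natural use of the data even though no fit is specified.

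Four stronger readings are tempting, and the documents do not support them.

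- **Norketamine is hit harder, by 2^(0.25/1.2), or 15.5%.** This treats it as dosed directly. It is formed from ketamine, which by the protocol's figures clears more slowly, so its late decline follows ketamine. With one compartment each for parent and metabolite and instant absorption, the shift is 2.3%, 6.6% and 7.8% at 3, 6 and 9 h for a 2.1 h parent, below ketamine's 8.6%.
- **Random timing error adds 5.9-11.8% to the slope (SD/√18).** This gives home-type deviations to pumps that are done on site.
- **The Screening Script is a third conflicting rule.** Its "You would spend at least 10 hours at our comfortable offices" does not mention home pumping. It fits the Procedures text: arrival 30 minutes before zero plus a 9 h pump is already about 10 hours.
- **The offset shifts the hour at which feeding resumes.** That decision rests on detectability on a 3-hour grid. If levels only fall, milk undetectable at 8.75 h is also undetectable at 9 h.

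**Conclusion.** The point holds as a defect in the definition and recording of time. On the chart as written, every post-dose pump is 15 minutes short of its label in time after dosing, and the one-hour check contradicts the Procedures text.

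The effect on milk levels is conditional: it arises if chart hours are analysed as hours after dosing, which the half-life language implies but no text states. It is then about 6-9% for point ketamine levels. For pooled milk it is 5-6% low at the first pump and 6-9% high later, with a fitted half-life about 7% too long at 2.1 h. The pooled figures depend on the three assumptions given with them. With point sampling the half-life is not biased.

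The missing clock times are the larger gap, because departures from the planned schedule could not be corrected. For the 9 h home pump this is worth 4.2% or 8.3% in the elimination rate, under assumed SDs of 15 or 30 minutes. A reader might infer that every reported level will certainly be assigned to the wrong time; the documents do not go that far.

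**What to change.** - Define time zero for the analysis as the injection, and state chart times as hours after injection.
- Reconcile the chart with the Summary of Research Design on the milk sampling hours, and with the Procedures text on the one-hour blood pressure and heart rate check.
- Record the clock time of the injection and the start and end of each expression, on the aliquot label and in the Excel matrix, for home pumps as well as those on site.
- Add actual time after injection to the variables in Data Analysis, and report, graph and analyse levels by it.
- Reconcile the Procedures text and the chart's Home row on when pumping may take place at home.

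The cost is a few clock times per sample and some rewording. It needs no extra samples and no change to dose or to the rule for resuming feeding.

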Subjects will refrain from eating and drinking 3-4 hours before receiving ketamine, this to

prevent stomach contents that may contribute to nausea, and reduce any risk of aspiration. Subjects are permitted one cup of coffee, juice or water at 3-4 hours prior if they are caffeine dependent. PROVIDED IN LAST VERSION

- 1) A urine pregnancy test will be conducted prior to each administration of ketamine.
- 1)
- 2) A first subject in the study will have milk collected at 0, 3, 6, 9, 12 and 15 hours to determine if these intervals are sufficient to characterize a basic pharmacodynamic profile. If there is a negligible quantity in the samples as the time frame proceeds, the lab will not analyze subsequent samples. Once determined, the study will proceed with the remaining 3 subjects at the intervals projected from the first subject. The lab will process the samples from the first subject as rapidly as possible to enable continuation of the study. Breast milk will be collected until ketamine levels are undetectable. If significant amounts of ketamine are found in samples from the 3 subsequent subjects at the last interval determined by the profile of the first subject, additional time frames for collection will be added. If necessary, the process will be repeated to fully document pharmacokinetics.

As real time testing of ketamine content in breastmilk is not possible, the first subject will be the exemplar for the timing of the resumption of breast feeding based on the data obtained, such as not detectable at 9 hours, hence breast feeding may resume. For that first subject, breast feeding may resume at 18 hours, which corresponds to 9 half-lives for ketamine, 4 half-lives being the accepted timing for the absence of a molecule. This will be confirmed by lab testing as quickly as possible for the first subject.

- 3) Pumping of breast milk will be for a full expression so as not to influence concentrations in subsequent sampling intervals. The volume of breast milk will be quantified for each expression.
- 4) Milk will be refrigerated in sterile containers and aliquots of one ounce will be brought to the lab refrigerated as soon as possible. A second aliquot of each

expression will be frozen in the event of loss or spoilage of the first aliquots, site to be determined.

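### The lab may stop assaying the first subject's milk at an undefined 'negligible' level while collection runs to 'undetectable', so time to non-detection may go unobserved in milk already collected

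*Combined protocol and SAP*

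**What the plan says.** Under Procedures, and again in Methods item 2, the first subject gives milk at 0, 3, 6, 9, 12 and 15 hours "to determine if these intervals are sufficient to characterize a basic pharmacodynamic profile". Both places then carry the assay-stop rule: "If there is a negligible quantity in the samples as the time frame proceeds, the lab will not analyze subsequent samples".

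The end of collection is put differently. Procedures says "The collection at 3 hour intervals will continue until ketamine levels are undetectable", and Methods item 2 says "Breast milk will be collected until ketamine levels are undetectable". A third term governs added intervals. Procedures begins that sentence "If the study determines that significant amounts of ketamine remain in breast milk after 9 hours and 3 intervals", and Methods item 2 uses the same idea for the later subjects.

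The first subject's results are then used twice. For the schedule: "Once determined, the study will proceed with the remaining 3 subjects at the intervals projected from the first subject". For feeding, Methods item 2 makes her the exemplar for when breastfeeding resumes and gives as its example a result that is not detectable at 9 hours.

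Methods item 1 has the lab prepare a standard for ketamine and norketamine. It gives half-lives of 2.1 h and 1.2 h, and a planning value of 3 h. No detection or quantification limit appears anywhere in the document.

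**The concern.** Assay and collection stop on two different words, neither of them quantified. Taken literally, the lab may stop at a low positive value while pumping continues. The later samples would then exist but carry no result. The low value itself would be reported. What would be missing is the decline after it and the first non-detected sample.

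The two rules also do not fit together, because milk that is not assayed cannot be shown to be free of ketamine.

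This matters because of who the first subject is. She is one of four, but her profile fixes the sampling times of the other three and is the reference for resuming feeding. Her late samples are the ones that answer those questions, and they are the ones the rule allows to be skipped.

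The rule also names no analyte. If the lab stops on ketamine alone, norketamine measurement may end with it.

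**Working it through.** The plan has no figure of its own to reproduce here. The check compares the wording of the rules, then asks how many samples the rule could remove.

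**Step 1: do other sentences close the gap?**

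- Added time frames for the later subjects are triggered by 'significant amounts' "at the last interval determined by the profile of the first subject, additional time frames for collection will be added". That trigger is not quantified and concerns subjects 2 to 4, not the first subject's unassayed milk.
- "If necessary, the process will be repeated to fully document pharmacokinetics" is discretionary and has no trigger.
- Methods item 2 promises laboratory confirmation for the first subject but names no sample time and no limit.
- Methods item 4 freezes a second aliquot in case the first is lost or spoiled. It does not provide for assaying skipped samples later.

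None of these requires the skipped milk to be measured.

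**Step 2: how many samples could be skipped?**

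Inputs from the protocol are post-dose times of 3, 6, 9, 12 and 15 h (5 samples per session) and ketamine half-lives of 2.1 h and 3 h. Two things are assumed: milk declines mono-exponentially from the 3 h sample, and 'negligible' is some percentage of the 3 h level. The documents give no value for that percentage, so a range is shown.

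Level relative to the 3 h sample = 2^(−(t − 3)/half-life).

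| Time | Half-life 2.1 h | Half-life 3 h |
|---|---|---|
| 6 h | 37.2% | 50% |
| 9 h | 13.8% | 25% |
| 12 h | 5.1% | 12.5% |
| 15 h | 1.9% | 6.25% |

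The last sample assayed is the first one at or below the assumed cut-off.

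| Assumed cut-off | Skipped, half-life 2.1 h | Skipped, half-life 3 h |
|---|---|---|
| 50% | 3 (9, 12, 15 h) | 3 (9, 12, 15 h) |
| 25% | 2 (12, 15 h) | 2 (12, 15 h) |
| 20% | 2 (12, 15 h) | 1 (15 h) |
| 10% | 1 (15 h) | 0 |
| 5% or lower | 0 | 0 |

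The range is therefore 0 to 3 of 5 per session. Three are skipped only if a 6 h sample at 37% to 50% of the 3 h level is called negligible. That is hard to credit unless the 3 h level was itself close to nothing, so 0 to 2 is the more plausible range.

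**Step 3: what is lost when samples are skipped?**

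Take a cut-off of 25% and a detection limit of 2% of the 3 h level (both assumed).

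- Half-life 2.1 h: the 12 h sample (5.1%) is detectable but unassayed. The 15 h sample (1.9%) would have been the first non-detect and is also unassayed. Time to non-detection is not observed.
- Half-life 3 h: both skipped samples (12.5% and 6.25%) are detectable and unassayed.

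If the cut-off equals the detection limit, every skipped sample is below it, and no detectable ketamine is lost.

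**The case against.** The best defence is that the text, read as a whole, intends follow-up to non-detection. Collecting until ketamine is undetectable can only be carried out from assay results, and the protocol's own example is a not-detectable result. On that reading 'negligible' merely spares the lab from running samples after the drug has gone. This is a fair reading, and if the lab adopts it no detectable ketamine is lost. But the document does not say so, and the collection sentence governs pumping, not assay.

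It is also fair that the loss may be recoverable. Frozen aliquots exist, confirmation is promised and repetition is allowed. These soften the point without removing it, since none obliges anyone to assay the skipped milk.

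Three stronger inferences are tempting and are not supported:

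- **That a definite number of hours is lost.** That would need the ratio of 'negligible' to the detection limit, and the documents give neither.
- **That an early stop spoils a planned slope or half-life estimate.** Data Analysis plans quantities, graphs and correlations. It describes no log-linear fit.
- **That non-detection is the stated criterion for the later subjects' last sampling time, so their schedule would be wrong.** The protocol says only that this time comes from the first subject's profile, and it allows time frames to be added.

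**Conclusion.** The point holds as a conditional one. The plan permits late first-subject samples to be collected and left unmeasured, because the assay-stop and collection-stop terms are neither defined nor linked. Whether data are lost depends on how the lab reads 'negligible'. The effect is 0 to 3 of 5 post-dose samples per session, with 0 to 2 more plausible. Those counts rest on mono-exponential decline at the stated half-lives and on assumed cut-offs.

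The document does not show that a loss is intended or certain. It shows that one sentence allows it in the subject on whom the rest of the schedule depends, and that whether norketamine is covered is left open. That is enough to justify a wording change before the first subject's samples reach the lab.

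**What to change.** In Procedures and in Methods item 2, delete the clause that stops the lab analysing later samples. Assay every sample collected from the first subject for ketamine and norketamine. If a stopping rule is kept, let it apply only after a result below the assay's validated detection limit for both analytes, and use that same limit to define 'undetectable' in the collection rule. The standard is still to be prepared, so the protocol can refer to the validated limit and record its value before the first sample is run.

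Report time to non-detection for each analyte as the interval between the last detected and first non-detected sample, or as later than the last sample if the analyte is still detected there. The change does not guarantee that non-detection is reached by 15 h. At a 3 h half-life the 15 h sample is still 6.25% of the 3 h level.

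The assay-stop and collection-stop sentences in the two sections must be reconciled. The trigger for adding intervals and any clinical rule on resuming feeding are left to the sponsor.

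The cost is wording plus at most about 1 to 3 extra samples assayed per first-subject session (2 to 6 over her two sessions), from milk already collected. Turnaround of her results may be slightly slower, and the plan wants those results quickly.

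### Women 2-4 stop pumping at a time projected from one woman, and the plan's add-on rule cannot complete a session that has already been cut short

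*Combined protocol and SAP*

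**What the plan says.** Two places set the end of collection by the assay result. Procedures states "The collection at 3 hour intervals will continue until ketamine levels are undetectable", and Methods, item 2, states "Breast milk will be collected until ketamine levels are undetectable".

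Methods, item 2, then explains why this cannot work as a live stopping rule: "As real time testing of ketamine content in breastmilk is not possible". The plan uses the first woman as a pilot instead. She pumps at 0, 3, 6, 9, 12 and 15 h, and then "the study will proceed with the remaining 3 subjects at the intervals projected from the first subject". The Procedure Timing Chart lists pumps at 0, 3, 6 and 9 h, a 12 h pump only if needed, and no 15 h pump.

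There is a safeguard. If significant ketamine is still present in the later women at the "last interval determined by the profile of the first subject, additional time frames for collection will be added", and "If necessary, the process will be repeated to fully document pharmacokinetics". Procedures has a similar rule for ketamine persisting after 9 h. Fast assay is promised for the first woman: "The lab will process the samples from the first subject as rapidly as possible to enable continuation of the study". No equivalent promise is made for the other three.

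**The concern.** The stated end point and the operating rule differ for three of the four women. They stop when the first woman's profile suggests they can, and a woman who clears more slowly may stop while her milk still contains measurable ketamine. By the time the assay shows this, her later milk from that session was never collected.

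This bears on the question set in Procedures: "This study will assess if the rapid elimination of ketamine facilitates a short and tolerable suspension of breastfeeding". A profile that ends while ketamine is measurable gives only a lower bound on that woman's time to undetectable, plus a slope. With four women planned, each is a quarter of the data. The rule for turning the first woman's profile into times for the others is not stated, and neither negligible nor significant is defined.

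**Working it through.** **Inputs.** Ketamine half-life: 2.1 h (cited in Methods, item 1), 2.5 to 3 h (Summary of Research Design), and 3 h (the value the study adopts as conservative). Mark for absence: 4 half-lives (Methods, item 2). First woman's grid: to 15 h. Gap between sessions: at least 3 days, preferably a week. Assumption: one-phase decline, with milk following the quoted half-life.

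**The plan's own figure.** Methods, item 2, equates 18 h with 9 half-lives. 18/2.1 = 8.57, which rounds to 9, so the figure reproduces at the 2.1 h half-life. At the adopted 3 h it is 18/3 = 6, still above 4.

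**Fraction left at a given last pump.** Formula: 2^(-t/half-life).

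| Half-life | 4 half-lives | Left at 9 h | Left at 12 h | Left at 15 h |
|---|---|---|---|---|
| 2.1 h | 8.4 h | 5.1% | 1.9% | 0.7% |
| 2.5 h | 10 h | 8.2% | 3.6% | 1.6% |
| 3 h | 12 h | 12.5% | 6.25% | 3.1% |

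The chart places the injection 15 minutes after the zero-time pump. Counting from the injection barely changes the range: at 9 h, 2^(-8.75/2.1) = 5.6% to 2^(-8.75/3) = 13.2%; at 15 h, 2^(-14.75/2.1) = 0.8% to 2^(-14.75/3) = 3.3%.

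**How much slower must a later woman be?** Suppose the first woman becomes undetectable between her 6 h and 9 h pumps, that is, 5.75 to 8.75 h after injection. At the same dose and starting level, a later woman is cut short when her half-life exceeds the first woman's by the ratio (last pump - 0.25)/(first woman's crossing time).
- Last pump at 9 h: 8.75/8.75 = 1.00 to 8.75/5.75 = 1.52, so 0% to 52% longer.
- Last pump at 15 h: 14.75/8.75 = 1.69 to 14.75/5.75 = 2.57, so 69% to 157% longer.

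The half-lives in the protocol differ by 3/2.1 = 1.43, or 43%. That is a spread between sources, one of them a study in children, and not a measure of variation between lactating women.

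**When can the add-on rule help?** Samples are to be picked up by the next day where possible. Session 1 results can then shape session 2 if the assay takes under about 3 - 1 = 2 days at the minimum gap, or 7 - 1 = 6 days at the preferred gap. They can also shape a later woman's sessions. They cannot change the session that produced them, and a shortened second session has no planned later session for the same woman.

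**The case against.** The plan sees the problem and provides for it, and that stands. Methods, item 2, and Procedures both add collection times when ketamine persists, so what remains is the affected session only. The stated purpose, measuring presence and concentration in milk, also survives a missing tail, and a slope can still be estimated.

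A reader might infer more than the documents support:

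- **That a 9 h stop is planned for women 2-4.** It is not. Their times are projected from a woman sampled to 15 h, nothing excludes a margin, and the chart allows a 12 h pump. The mention of 9 h in Methods, item 2, is an example about resuming breastfeeding.
- **That truncation is likely in some known proportion.** If the four women are exchangeable, the chance that at least one later woman is slower than the first is 1 - 1/4 = 75%. Slower does not mean truncated, and the frequency of truncation cannot be derived without the detection limit, turnaround and between-woman variation.
- **That 18 h should be mandatory.** Taking 4 half-lives as the mark after 0.5 mg/kg, a 3 h half-life and linear kinetics, the same level after 1.0 mg/kg falls at 0.25 + 5 x 3 = 15.25 h. A 15 h pump misses it by 15 minutes (3.3% left against 3.1%). The mark is also a relative one and does not fix a detectable level.
- **That repeating the process authorises a further injection.** The wording does not say so, and the Screening Script and the reimbursement section describe two sessions per woman.
- **That infants are shown to be at risk.** This point concerns completeness of the profile and establishes no harm.

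**Conclusion.** The concern holds in a limited form. Collection until undetectable cannot be applied to women 2-4 during a session, their stopping time rests on one woman, and the planned remedy arrives too late for the session that triggers it. If a 9 h stop were projected, about 5% to 13% of ketamine would remain at the last pump, against about 1% to 3% at 15 h. These figures rest on a one-phase decline, on milk following the quoted half-lives, and on a 9 h stop that is hypothetical. The percentages are not probabilities of truncation. This is a modest design improvement that would sharpen the answer on how long breastfeeding must be suspended. No error rate or sample size is affected.

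**What to change.** 1. Have women 2-4 collect and store milk on the first woman's full grid (0, 3, 6, 9, 12 and 15 h) in both sessions.
2. Assay each woman's samples in time order and leave later aliquots unassayed once ketamine is undetectable. The plan already lets the lab skip late samples when quantities become negligible.
3. Report any profile still positive at its last sample as truncated, with that time and value.
4. Keep the add-on rule for sessions not yet held.

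The cost is one extra pumping per session compared with the charted 12 h pump (15 h), or two compared with a 9 h stop (12 and 15 h). Some fall in the evening or at night, mostly at home, which the protocol already permits. The infant needs a somewhat larger milk reserve. The Screening Script, which mentions at least 3 to 4 pumpings, would need to say six, and the lab should confirm that storage suits the unassayed aliquots.
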